JRMO	Joint Research Management Office
NHS REC	National Health Service Research Ethics Committee
NHS R&D	National Health Service Research & Development
Participant	An individual who takes part in a clinical trial
PBMC	Peripheral blood mononuclear cells
PI	Principal Investigator
PIS	Participant Information Sheet
QMUL	Queen Mary University of London
REC	Research Ethics Committee
ROC	Receiver Operating Characteristic
SAE	Serious Adverse Event

[figure not shown]
3. Signature page

Chief Investigator Agreement

The study, as detailed within this Research Protocol, will be conducted in accordance with the principles of Good Clinical Practice, the UK Policy Framework for Health and Social Care Research, and the Declaration of Helsinki and any other applicable regulations. I agree to take responsibility for the statistical analysis and oversight of this study.

Chief Investigator Name: [name]

Signature:

Date: 20th June 2022

4. Summary and synopsis

Short title	IDentification of EGPA Autoantigens (IDEA)
Methodology	Laboratory-based research study using blood and sputum samples from healthy controls and patients with EGPA, Severe Eosinophilic Asthma and other eosinophilic diseases.
Objectives / aims	To determine the presence, or not, of auto-antibodies to self-peptides in severe eosinophilic asthma and EGPA.
Number of participants	120 participants (90 patients and 30 healthy controls)
Inclusion and exclusion criteria	
Major Inclusion Criteria:
 
Patients: Patients with Severe Eosinophilic Asthma and/or EGPA and/or eosinophilic COPD and/or eosinophilic oesophagitis, age 18 yo and over, and able to give consent.
 
Healthy Controls: age 18 yo and over, and able to give consent.
 
Exclusion criteria:
 
Pregnancy; anaemia; rituximab, plasmapheresis or IVIG infusion ever

Study duration	30 months (18 months recruitment)

5. Introduction

5.1. Background

The pivotal importance of eosinophils in the pathology of severe asthma and eosinophilic granulomatous polyangiitis (EGPA) is increasingly evident given the success of anti-eosinophil biologic therapies. The source of eosinophil stimulating IL-5 in severe asthma is now thought to be ILC2 cells. However the persistent chronicity of the airways inflammation in the absence of an exogenous stimulus in most patients is unexplained and of major research importance. This suggests the presence of an endogenous stimulus of persistent auto-reactive airways inflammation - an auto-immune hypothesis for severe asthma pathology - which with molecular spread could then potentially lead to the systemic disease of EGPA (Mukherjee and Nair 2018).

Auto-antibody responses have been reported in patients with asthma (Mukherjee and Nair 2018). For example Lott and colleagues have detected auto-antibodies to type V collagen in asthmatic individuals (Lott, Sehra et al. 2013). Similarly Liu and colleagues have reported auto-antibodies to type V collagen in asthmatic patients, as well auto-antibodies to other proteins such as Activin A receptor, with clinical correlates to markers of asthma severity (Liu, Subramanian et al. 2012). However auto-antibodies within the pulmonary compartment, as detected in sputum, may be more important than auto-antibodies in serum (Qin, Long et al. 2019). In particular auto-antibodies to eosinophil peroxidase in sputum is a feature of severe eosinophilic asthma (Mukherjee, Bulir et al. 2018).

Anti-neutrophil cytoplasmic antibodies (ANCA), especially anti-myeloperoxidase antibodies, are present in a proportion of patients with EGPA but absent in a similar proportion. Similar perinuclear ANCA is also present in inflammatory bowel disease. These issues raise the question of whether ANCA in EGPA is an epiphomenon or pathological.

Previous research at our centre and with collaborators has shown that post-translational modification of potential auto-antigens is a key step in breaking self-tolerance and development of autoimmune disease (Ryan, Nissim et al. 2014) (Eggleton, Nissim et al. 2013). For example we have shown auto-antibodies to oxidised type II collagen are much more frequent than those to native type II collagen in rheumatoid arthritis (Nissim, Winyard et al. 2005). Similarly in type 1 diabetes mellitus auto-antibodies to insulin that has undergone oxidative post-translational modification are significantly more common than those to native insulin (Strollo, Vinci et al. 2015).

Oxidative stress, implicated in the formation of oxidised auto-antigens, is a major feature of uncontrolled asthma inflammation (Mak, Ho et al. 2013). However, to date the potential role of modified auto-antigens in the airways has not been studied in severe eosinophilic asthma, EGPA and other related diseases.

In this project we will look for auto-antibodies to relevant proteins both in native form and importantly in post-translationally modified forms. Potential modified auto-antigens are eosinophil proteins (analogous to the cytoplasmic neutrophil proteins identified in vasculitides such as Granulomatosis with Polyangiitis (formerly known as Wegener's) and alternatively structural proteins such as collagen V. As well as advancing our understanding of asthma pathology, identifying a serum auto-antibody that could then be used as a clinical blood test, analogous to anti-CCP antibodies in rheumatoid arthritis, may revolutionise diagnosis of severe eosinophilic asthma and EGPA. There is a considerable burden of undiagnosed severe eosinophilic asthma in part due to difficulties in definitive diagnosis and a diagnostic blood test would help diagnose these patients, allowing them to receive necessary treatment.

We have previous experience of identifying novel autoantigens in Systemic Lupus Erythematosus (SLE) (Lewis et al. 2018), using an advanced protein microarray developed by Oxford Gene Technology, now known as Sengenics. This protein microarray technology benefits from using correctly folded proteins with preserved native epitopes, and the technology permits on chip modification of proteins such as citrullination or oxidation.

5.2. Rationale

We hypothesise the presence of auto-antibodies to self-peptides in severe eosinophilic asthma and EGPA, underpinning persistent airways inflammation in patients with severe eosinophilic asthma refractory to standard therapies. In particular we hypothesise the auto-antigens will be to eosinophil proteins and/or basement membrane proteins that are post-translationally modified.

In this study we will collect blood and sputum samples from well-phenotyped patients with EGPA, severe eosinophilic asthma and other eosinophilic diseases. The presence or not of auto-antibodies to relevant self-peptides, in native and post-translationally modified form, will be determined with appropriate assays.

5.3. Risks / benefits

Previous research has shown the profound benefit of translational research and potential for such studies to advance our understanding of disease leading to new treatments. The only participant involvement in this study is the consent process, the blood donation (venipuncture and collection of up to 50 mls blood in to sterile containers using standard phlebotomy practice at the recruiting NHS Trust), and sputum donation in patients producing sputum. As such risks are low and potential benefits high.

6. Study objectives

We will approach the research question with parallel agnostic and targeted approaches.

In the agnostic approach the presence of auto-antibodies in patient serum and sputum to inactive and activated eosinophils, with and without post-translational modification, will be examined by indirect immunofluorescence.

In the targeted approach we will examine by ELISA the presence/absence of antibodies to pre-selected candidate eosinophil and base membrane proteins both in native form and post-translationally modified. Proteins to examine will be chosen based on literature review (e.g. eosinophil peroxidase and collagen V) and eosinophil-specific proteins identified by FANTOM5 geneset analysis (FANTOM Consortium et al. 2014).

Both blood and sputum samples from highly-characterised patients with severe eosinophilic asthma and/or EGPA will be examined given the possibility of compartment-specific immune responses.

Once candidate auto-antigens have been identified in the selected group of patients with severe eosinophilic asthma and EGPA we will then examine their prevalence in serum samples from a wider selection of patients with eosinophilic airways diseases including mild-to-moderate asthma, severe eosinophilic asthma, EGPA, nasal polyposis and eosinophilic COPD as well as healthy controls. Length of disease, atopy, presence/absence nasal polyps, gender, age will be examined as co-variates. Correlations with highest blood eosinophil counts, requirement for oral corticosteroids and presence of other auto-antibodies, e.g. anti-MPO ANCA, will be examined. In particular we will look for the presence of novel autoantibodies in specific patient subsets: i) ANCA negative, ii) ANCA positive by immunofluorescence but negative for anti-MPO and anti-PR3 antibodies, iii) ANA positive but ANCA and ENA negative; since patients in all three groups may have novel, as yet undetermined autoantibodies. ROC AUC analyses will be conducted to ascertain the predictive value of blood auto-antibodies for diagnosis of eosinophilic airways disease.

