6.1. Study Outcomes / Endpoints

Primary objectives

- The presence of serum and/or sputum auto-antibodies to eosinophil and/or basement membrane proteins will be established in severe eosinophilic asthma and EGPA cohorts, and patients with other asthma phenotypes and related eosinophilic diseases.
- Whether auto-antibodies to post-translationally modified self-antigens are more prevalent than to native self-antigens will be examined, and which post-translational

modifications are important to be studied (including particulate matter air pollution as a potential combined stimulus of eosinophil activation and protein modification).

Primary outcomes

- Correlations of auto-antibodies to clinical variables such as spirometry (FEV1 % predicted), pattern of organ involvement, age of onset, requirement for maintenance of oral corticosteroids, eosinophil count, highest recorded eosinophil count and FeNO will be studied.
- Predictive ability to diagnose severe eosinophilic asthma / EGPA of relevant auto-antibodies will be examined by ROC AUC analysis.

Secondary outcomes

- Exploratory Outcomes: Further experimental assays may be conducted to examine immunological mechanisms underpinning associations of auto-antibodies to disease.

7. Study population

90 patients under the care of the Barts Health NHS Trust and Royal Free London NHS Trust with severe eosinophilic asthma, EGPA, eosinophilic COPD and other related pathologies will be recruited.

At least 60 patients will have severe eosinophilic asthma and/or EGPA, and will be recruited from the regional North Central and East London Severe Asthma Service, the Royal Free London NHS Trust and from the Barts Arthritis Centre, with multi-disciplinary consensus diagnoses of severe eosinophilic asthma and/or EGPA respectively. Patients will be phenotyped with blood leucocyte differential, lung function tests and FeNO as appropriate in conjunction with detailed medical history.

Up to a further 30 patients with milder asthma, other vasculitides, eosinophilic COPD, and/or eosinophilic oesophagitis will be recruited from other clinics at Barts Health NHS Trust and the Royal Free London NHS Trust.

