In a future extension of this research our intention is to verify positive findings with samples from a replication sample of patients with severe eosinophilic asthma from the wider network of the North Central and East London Severe Asthma Service (principally through our satellite clinic at Royal Free London NHS Trust). These samples will be collected under a separate ethics application.

30 healthy controls will be recruited from volunteers at Queen Mary University of London via poster advertising. Healthy controls will also be recruited from Barts Health NHS Trust and the Royal Free London NHS Trust.

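### If candidates are chosen and then scored in the same severe eosinophilic asthma/EGPA patients, the primary-outcome AUC is biased upward, probably modestly, and section 10.2 makes no allowance for it

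*Combined protocol and SAP*

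**What the plan says.** All references are to the combined protocol and SAP.

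- **Choosing candidates (section 6).** The ELISA arm starts from "pre-selected candidate eosinophil and base membrane proteins both in native form and post-translationally modified", drawn from the literature and a gene-expression resource. An agnostic immunofluorescence arm runs in parallel. Then: "Once candidate auto-antigens have been identified in the selected group of patients with severe eosinophilic asthma and EGPA we will then examine their prevalence".
- **Scoring candidates (section 6).** The second step is carried out "in serum samples from a wider selection of patients with eosinophilic airways diseases including mild-to-moderate asthma, severe eosinophilic asthma, EGPA, nasal polyposis and eosinophilic COPD", plus healthy controls, and "ROC AUC analyses will be conducted to ascertain the predictive value of blood auto-antibodies for diagnosis of eosinophilic airways disease".
- **Choosing the form (section 6.1).** A primary objective is: "Whether auto-antibodies to post-translationally modified self-antigens are more prevalent than to native self-antigens will be examined". Which modifications matter is also left to be found.
- **Outcome (section 6.1).** Under primary outcomes: "Predictive ability to diagnose severe eosinophilic asthma / EGPA of relevant auto-antibodies will be examined by ROC AUC analysis".
- **Who is available (section 7).** Of 90 patients, "At least 60 patients will have severe eosinophilic asthma and/or EGPA". The up to 30 others have milder asthma, other vasculitides, eosinophilic COPD or eosinophilic oesophagitis. There are 30 healthy controls.
- **Analysis (section 10.2).** ROC AUC is named, with no split, resampling, selection rule or correction.
- **Later use.** Section 10.1 says the study's data will be used to size larger studies. Section 7 intends, as a future extension under separate ethics approval, to "verify positive findings with samples from a replication sample of patients with severe eosinophilic asthma".

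**The concern.** A marker that goes forward because it looked strong in certain patients carries their favourable chance variation with it. If its AUC is then computed in a set containing those patients, that variation is counted again and the AUC is too high on average.

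Two choices here are made on study results: which candidates go forward, and which modified form matters. Drawing up the protein list from the literature and gene-expression data uses no study results and adds no optimism.

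The figure affected is a primary outcome. Section 10.1 does not say that the AUC will be used to size later studies. If it were, an inflated AUC would make them too small.

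**Working it through.** **1. Is overlap likely?** 90 patients less at least 60 with SEA/EGPA leaves at most 30, and the groups listed for those 30 contain no SEA or EGPA. SEA/EGPA patients in the wider set must therefore come from the same pool of at least 60, unless that pool is split. No section splits it, gives the size of the selected group, or names another sample source for this study.

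**2. Inputs.** The plan has no AUC, precision or power figure to reproduce.

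- From the documents: 60 cases (section 7) and 30 healthy controls (section 7). Section 14 names six proteins (EPX, ARFIP1, BCL2A1, PPCDC, SLC12A6, collagen V) in up to four forms (native, oxidised, citrullinated, particulate-modified), so 6 × 4 = 24 markers. The list is open-ended.
- Assumed: normally distributed markers, correlation 0.5 between forms of one protein, the true AUCs, and the selection rule.

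**3. Method.** A marker with true AUC A has its case mean shifted by √2 × z(A), where z is the standard normal quantile. Bias = apparent AUC minus true AUC of the chosen marker, averaged over 2,000 simulated studies (800 for the several-candidates rule). Under that rule, a marker goes forward if at least 10% of cases exceed the control 95th percentile, and bias is averaged over the markers forwarded. In the single-marker columns, the first figure selects in all the same people and the second selects in half of them; both score in everyone.

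| True AUCs of the 24 markers | Several forwarded on case reactivity | One: highest case mean | One: best AUC |
|---|---|---|---|
| All 0.50 | +0.031 | +0.067 / +0.048 | +0.119 / +0.083 |
| All 0.65 | +0.005 | +0.061 / +0.041 | +0.108 / +0.075 |
| Spread 0.50–0.65 | +0.011 | +0.043 / +0.033 | +0.093 / +0.070 |
| Spread 0.50–0.80 | +0.004 | +0.022 / +0.019 | +0.059 / +0.046 |
| Three at 0.75, rest 0.50 | +0.007 | +0.023 / +0.016 | +0.044 / +0.034 |
| One at 0.75, rest 0.50 | not run | +0.001 / +0.001 | +0.005 / +0.027 |

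Forwarding the top half by case mean gives +0.006 to +0.029 on average.

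**4. Checks.**
- Selecting in one half and scoring only in the other: within 0.006 of zero in every setting.
- Averaging over all 24 markers, as when all are reported: within 0.001 of zero.
- Cross-validation with selection repeated in each fold (best-AUC rule, all markers truly 0.65): apparent 0.760, cross-validated 0.652.
- 60 v 60, with the other 30 patients added to the comparator: +0.02 to +0.07 for highest case mean.
- 48 markers, all null, correlation 0.7: +0.074 for highest case mean, +0.135 for best AUC.

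**5. Precision.** Null SE of an AUC = √[(n₁ + n₀ + 1) / (12 n₁ n₀)].
- 60 v 30: √(91/21,600) = 0.065
- 30 v 30 (only cases split): √(61/10,800) = 0.075
- 30 v 15 (both split): √(46/5,400) = 0.092
- Nested cross-validation at 60 v 30 (simulated, all null): SD 0.078

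**6. If a later study were sized on this AUC.** Hanley–McNeil variance, 2:1 allocation, two-sided 5%, 90% power against 0.5. A true AUC of 0.65 needs 165 people. Planning on 0.67 gives 126 people and true power of 80%; on 0.69, 102 and 71%; on 0.71, 81 and 60%.

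**The case against.** - **Several candidates, not one winner.** Sections 6 and 6.1 speak of candidates and relevant auto-antibodies in the plural. The natural reading is that every antigen showing reactivity goes forward. This stands, and it is why the several-candidates column comes first. Outside the all-null setting, the threshold rule gives about +0.01 or less, well below the SE of 0.065.
- **Overlap is inferred.** A reader might conclude that the protocol re-uses the same patients; it does not say so. The wider set also lists nasal polyposis, which is neither a recruited group in section 7 nor an eligible diagnosis in section 7.1, so that set does not map neatly onto the recruits. This stands as a caveat, but no other source of samples is named.
- **Different assay or compartment.** Discovery includes immunofluorescence and sputum, while the follow-up is in serum. Where selection rests on another measurement, less error is shared and the bias is smaller than simulated. This stands.
- **Pilot status and planned replication.** Both temper what readers should conclude, but neither changes the AUC reported as this study's primary outcome.
- **A heavy remedy.** Splitting cases and controls raises the SE from 0.065 to 0.092, an increase of 0.027 that can exceed the bias removed. Nested cross-validation needs every candidate assayed on everyone, which works against a staged design. This stands, so neither should be compulsory.

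**Conclusion.** The point holds conditionally. If discovery patients are scored again, markers or forms carried forward on study results have an AUC biased upward, and section 10.2 has nothing to prevent or disclose it. With 24 markers and 60 v 30, the expected bias is about 0.00 to +0.03 on average if several candidates go forward on case reactivity, and +0.02 to +0.07 if one is singled out by highest case reactivity. It is near zero if one marker clearly dominates under these case-based rules, or if all tested markers are reported.

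A reader might infer inflation of about +0.12, and a later study planned on an AUC of 0.76 with 51 people and 40% power when the truth is 0.65. The documents do not support that as the expected outcome. It needs one marker picked by best AUC in the same people, with all markers equally good, and then used for sizing. Section 14 does include healthy controls in the immunofluorescence, so selection using controls is possible, but no such rule is described. Use of the AUC for sizing is possible under section 10.1 but not stated.

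The direction is secure if overlap occurs and several markers compete. The size rests on the assumed marker count, correlation, true AUCs and rule, so confidence is moderate. This is a worthwhile, inexpensive improvement, not a flaw that undermines the study.

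**What to change.** Add to section 10.2:

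1. Report the AUC with a confidence interval for every candidate and form tested by ELISA in cases and controls, not only those selected.
2. For any marker or form singled out from study results, give as the main figure an AUC that accounts for selection. Where all candidates were assayed on all participants, use cross-validation or bootstrap with the selection repeated inside each resample. Otherwise, compute the AUC in cases not used for discovery; all controls may be kept if selection used cases only.
3. If neither is feasible, label the in-sample AUC as exploratory and uncorrected for selection, and do not size later studies from it.

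Item 2 requires the discovery group, the rule for calling something a candidate, and the ROC case and comparator groups to be stated. The ROC target now differs between sections 6, 6.1 and 10.2; that is missing detail and adds nothing to the size of this point.

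**Cost.** Protocol wording and a short analysis script; no new participants. Item 1 uses data already collected. Under item 2 the AUC will be slightly lower and its interval wider: null SE about 0.065 rising to 0.075 (cases split only), 0.08 (nested cross-validation) or 0.09 (both groups halved). Resampling costs extra ELISA plates if the assays would otherwise be staged. Item 3 costs nothing but leaves the bias in the figure.

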6.1. Study Outcomes / Endpoints

Primary objectives

- The presence of serum and/or sputum auto-antibodies to eosinophil and/or basement membrane proteins will be established in severe eosinophilic asthma and EGPA cohorts, and patients with other asthma phenotypes and related eosinophilic diseases.
- Whether auto-antibodies to post-translationally modified self-antigens are more prevalent than to native self-antigens will be examined, and which post-translational

modifications are important to be studied (including particulate matter air pollution as a potential combined stimulus of eosinophil activation and protein modification).

Primary outcomes

- Correlations of auto-antibodies to clinical variables such as spirometry (FEV1 % predicted), pattern of organ involvement, age of onset, requirement for maintenance of oral corticosteroids, eosinophil count, highest recorded eosinophil count and FeNO will be studied.
- Predictive ability to diagnose severe eosinophilic asthma / EGPA of relevant auto-antibodies will be examined by ROC AUC analysis.

Secondary outcomes

- Exploratory Outcomes: Further experimental assays may be conducted to examine immunological mechanisms underpinning associations of auto-antibodies to disease.

7. Study population

90 patients under the care of the Barts Health NHS Trust and Royal Free London NHS Trust with severe eosinophilic asthma, EGPA, eosinophilic COPD and other related pathologies will be recruited.

At least 60 patients will have severe eosinophilic asthma and/or EGPA, and will be recruited from the regional North Central and East London Severe Asthma Service, the Royal Free London NHS Trust and from the Barts Arthritis Centre, with multi-disciplinary consensus diagnoses of severe eosinophilic asthma and/or EGPA respectively. Patients will be phenotyped with blood leucocyte differential, lung function tests and FeNO as appropriate in conjunction with detailed medical history.

Up to a further 30 patients with milder asthma, other vasculitides, eosinophilic COPD, and/or eosinophilic oesophagitis will be recruited from other clinics at Barts Health NHS Trust and the Royal Free London NHS Trust.

In a future extension of this research our intention is to verify positive findings with samples from a replication sample of patients with severe eosinophilic asthma from the wider network of the North Central and East London Severe Asthma Service (principally through our satellite clinic at Royal Free London NHS Trust). These samples will be collected under a separate ethics application.

30 healthy controls will be recruited from volunteers at Queen Mary University of London via poster advertising. Healthy controls will also be recruited from Barts Health NHS Trust and the Royal Free London NHS Trust.

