7.1. Inclusion criteria

- *Informed consent*
- *Age 18 years and over*
- *Patients:*
 - *Severe Eosinophilic Asthma*
(*with multi-disciplinary diagnosis as per ERS/ATS Criteria, blood eosinophils $\geq 0.3 \times 10^9/L$ on inhaled corticosteroids*); or
 - EGPA*
(*as per American College of Rheumatology (ACR) Criteria*); or
 - Eosinophilic COPD*
(*post-bronchodilator FEV1/FVC $< 70\%$ predicted, absence of bronchodilator reversibility, > 20 pack year smoking history, no medical history of current asthma, blood eosinophils $\geq 0.3 \times 10^9/L$*); or
 - Eosinophilic oesophagitis*
(*with diagnostic histology*); or
 - Granulomatosis with Polyangiitis (GPA, formerly called Wegener's)*
(*as per American College of Rheumatology (ACR) Criteria*)
- *Healthy Controls:*
 - *No acute medical illness.*
 - *No diagnosed chronic respiratory disease, allergy or infective condition, including no history of asthma.*
 - *No history of EGPA or other vasculitis,*
 - *No systemic immunosuppressive medication.*

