7.2. Exclusion criteria

- *Any inclusion criteria not met*
- *Known Pregnancy*
- *Anaemia*
- *Donation of more than 240mls blood in the last sixteen weeks (four months) to any other research study or as a donation to the National Blood Transfusion Service*
- *Rituximab, plasmapharesis or polyclonal immunoglobulin infusion (ever)*

8. Study design

Study Visit (Patients)

This is a single study visit encompassing patient recruitment, consent, data collection and provision of a peripheral blood sample with/without concurrent sputum sample, with no follow-up visits.

Patients will be recruited via Outpatient Clinics conducted at St Bartholomew's (Bart's) Hospital, The Royal London Hospital, and Mile End Hospital (all Bart's Health NHS Trust), Royal Free London NHS Trust, as well as from inpatients at these hospitals under the care of the Respiratory Medicine and Rheumatology teams (including those under other services needing inpatient respiratory medicine or rheumatology review).

Potential patients will be identified by their clinical team and invited to participate. If interested they will be given a Participant Information Sheet (PIS). Informed Consent and Screening will be undertaken by a GCP-trained member of the clinical team or GCP-trained researcher. An anonymised data collection case report form (CRF) will be completed by a member of the clinical team and a linked (anonymised) blood sample collected by a staff member trained in phlebotomy. If the patient is able to spontaneously produce sputum, and there is no clinical concern about TB infection, then they will be asked to cough a sample in to a sterile sample pot.

The linked anonymised CRF and samples will then be taken to the research laboratories at QMUL for immune cell analysis. Laboratory immunology studies will be conducted by as per protocol (Section 14) by a dedicated Post-Doctoral Research Assistant.

Study Visit (Healthy Controls)

There is a single study visit encompassing healthy control recruitment, consent, data collection and taking of blood sample, with no follow-up visits.

Healthy controls will be recruited at QMUL, Bart's Health and Royal Free sites via poster advertisement.

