10.2. Method of analysis

For the major body of translational laboratory experiments appropriate parametric and non-parametric tests will be conducted using GraphPad Prism. For experiments assessing associations of detected auto-antibodies to clinical variables, linear regression analyses will be undertaken in R, and ROC AUC analysis of capacity of serum auto-antibodies to detect severe eosinophilic diseases undertaken.

11. Ethics

The Chief Investigator will ensure that the study is carried out in accordance with the ethical principles of the UK policy framework for health and social care research (2017) and its subsequent amendments as applicable, as well as applicable legal and regulatory requirements.

The research team has no financial or other competing interests for this study.

Human genome (gDNA) analysis will not be conducted as part of this research project.

Clinically defined immunodeficiencies will not be tested for as part of the immunological analyses.

The CRF and samples for immunological analysis will be anonymised so donors are not known to the research team or anyone reviewing the analyses and results.

Invitation to participate and consent will be undertaken on the same day. Potential participants will be given as long as they require to review the PIS and ask questions before deciding whether to participate. The study clinical procedure (taking of a blood sample of 50ml maximum volume) carries minimal risk. Donor decisions to participate or not in the study will not affect their health or clinical care. We therefore feel this is an appropriate period for informed consent for this low-risk study. Requiring potential volunteers to come back on a second occasion to give informed consent and samples would not facilitate ethical recruitment of patients, many of whom need to travel significant distances to Barts Health/Royal Free Hospitals for appointments and many of whom have significant chronic ill health.

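### Milder asthma and nasal polyposis patients have no entry criterion although the plan means to study them, and the primary-outcome ROC for SEA/EGPA names no non-cases

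*Combined protocol and SAP*

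**What the plan says.** **ROC analyses.** The protocol mentions ROC analysis in three places.

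- Section 6.1, primary outcomes: "Predictive ability to diagnose severe eosinophilic asthma / EGPA of relevant auto-antibodies will be examined by ROC AUC analysis".
- Section 10.2, the only statistical methods text: "ROC AUC analysis of capacity of serum auto-antibodies to detect severe eosinophilic diseases undertaken".
- Section 6, study objectives: "ROC AUC analyses will be conducted to ascertain the predictive value of blood auto-antibodies for diagnosis of eosinophilic airways disease". The groups to be studied at that stage are "mild-to-moderate asthma, severe eosinophilic asthma, EGPA, nasal polyposis and eosinophilic COPD as well as healthy controls".

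None of the three says which participants are the non-cases.

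**Who is to be recruited.** Section 7 plans at least 60 patients with SEA and/or EGPA, and then: "Up to a further 30 patients with milder asthma, other vasculitides, eosinophilic COPD, and/or eosinophilic oesophagitis will be recruited". There are also 30 healthy controls. The first primary objective in section 6.1 covers SEA, EGPA and "patients with other asthma phenotypes and related eosinophilic diseases".

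**Who may be enrolled.** Section 7.1 lists five patient diagnoses: SEA, EGPA, eosinophilic COPD, eosinophilic oesophagitis and granulomatosis with polyangiitis (GPA). Healthy controls must have "No diagnosed chronic respiratory disease, allergy or infective condition, including no history of asthma", and no vasculitis. The first exclusion in section 7.2 is "Any inclusion criteria not met".

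**The concern.** There are two linked problems.

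**Eligibility.** Milder asthma is in the recruitment plan and in the primary objective, and nasal polyposis is in the section 6 plan. Neither is an entry diagnosis. If sites follow sections 7.1 and 7.2, the objective for other asthma phenotypes cannot be met. The ROC also loses a comparator that is clinically close to SEA.

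**The ROC comparison.** An AUC has no meaning until both groups are named. The study offers two very different sets of non-cases: volunteers screened free of asthma, allergy and chronic respiratory disease, and patients with other diseases. The primary AUC could be computed against either, or against both pooled, and the choice could be made after the data are seen. The background (section 5.1) hopes for a blood test that helps where diagnosis is difficult. That use needs separation from other disease, which healthy volunteers alone cannot show.

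**Working it through.** **Eligibility, side by side**

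| Group | Planned for study | Entry criterion in 7.1 |
|---|---|---|
| Milder or mild-to-moderate asthma | Sections 6 and 7; 6.1 through other asthma phenotypes | None |
| Nasal polyposis | Section 6 | None |
| Eosinophilic COPD | Sections 6 and 7 | Yes |
| Eosinophilic oesophagitis | Section 7 | Yes |
| Other vasculitides | Section 7 | GPA only |

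The COPD criterion requires no current asthma, and the healthy-control criterion requires no history of asthma, so neither admits milder asthma. Such a patient could enter only by also having another listed diagnosis. The synopsis (section 4) does not list milder asthma or nasal polyposis either.

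**ROC: inputs**

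- From the documents: at least 60 SEA and/or EGPA patients, up to 30 other patients and 30 healthy controls (60 + 30 + 30 = 120, which agrees with the synopsis).
- Assumed: an AUC against healthy controls of 0.90 or 0.80, a normally distributed marker with equal variance in each group, and other patients' mean a fraction f of the way from the healthy mean to the case mean. The documents give no AUC, so there is no figure to reproduce.

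**Formulas**

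- Case-to-healthy distance: d = √2 × Φ⁻¹(AUC vs healthy), which is 1.812 for 0.90 and 1.190 for 0.80.
- AUC vs others = Φ(d(1 − f)/√2).
- AUC vs pooled non-cases = (30 × AUC vs healthy + 30 × AUC vs others)/60. This is exact, because a pooled AUC is the size-weighted mean of its parts.
- 95% half-width = 1.96 × Hanley–McNeil SE for the AUC vs others, 60 against 30.

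Example, 0.90 and f = 0.5: Φ(1.812 × 0.5/1.414) = Φ(0.641) = 0.739. Pooled: (30 × 0.900 + 30 × 0.739)/60 = 0.820. Gaps: 0.900 − 0.739 = 0.161 and 0.820 − 0.739 = 0.080 (from unrounded values).

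| AUC vs healthy | f | AUC vs others | Pooled 30+30 | Healthy-only gap | Pooled gap | Half-width |
|---|---|---|---|---|---|---|
| 0.90 | 0 | 0.900 | 0.900 | 0 | 0 | 0.062 |
| 0.90 | 0.25 | 0.832 | 0.866 | 0.068 | 0.034 | 0.082 |
| 0.90 | 0.50 | 0.739 | 0.820 | 0.161 | 0.080 | 0.102 |
| 0.90 | 0.75 | 0.626 | 0.763 | 0.274 | 0.137 | 0.119 |
| 0.80 | 0 | 0.800 | 0.800 | 0 | 0 | 0.090 |
| 0.80 | 0.25 | 0.736 | 0.768 | 0.064 | 0.032 | 0.103 |
| 0.80 | 0.50 | 0.663 | 0.732 | 0.137 | 0.068 | 0.114 |
| 0.80 | 0.75 | 0.583 | 0.692 | 0.217 | 0.108 | 0.123 |

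The healthy-only gap exceeds the half-width from f = 0.50 upward in both cases. The pooled gap exceeds it only at f = 0.75 when starting from 0.90, and never when starting from 0.80.

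**Specimen.** Section 6.1 does not limit the specimen, section 6 says blood and section 10.2 says serum. The healthy-control visit in section 8 describes only a blood sample, although the immunofluorescence text in section 14 mentions sputum from patients and healthy controls. A healthy-control AUC is clearly supported for serum only.

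**The case against.** The strongest reply is that this is a pilot meant to reveal associations (section 10.1), with later replication intended under a separate ethics application (section 7). A healthy-control AUC is a legitimate first step in such work, and the comparator is merely unstated. Much of this stands, and it rules out several stronger readings.

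- *The plan will use healthy or pooled non-cases, so its AUC will be inflated.* No section commits to either choice, and the gap is zero if other patients resemble healthy people. The documents give no data on where their levels lie.
- *The three ROC targets contradict one another.* The term in section 10.2 is probably shorthand for SEA/EGPA, and section 6 may describe a separate, broader analysis. The terms are undefined, but a contradiction is not shown. Nor do the documents rank the section 6 ROC as secondary.
- *An inflated AUC will size the next study.* Section 10.1 says the data will inform later sample sizes. It does not say that the AUC will.
- *The study claims to validate a diagnostic test.* Section 5.1 states this as a hope, not as a claim for these data.

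Pilot status explains the absence of a power calculation. It does not explain a primary outcome with one of its two groups missing, and it does not touch the eligibility conflict.

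**Conclusion.** The point holds in two parts, and both should be corrected.

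**Eligibility.** The conflict is in the text and needs no assumption. Patients whose only relevant diagnosis is milder asthma or nasal polyposis cannot be enrolled as written, so the other-asthma-phenotypes part of the primary objective cannot be met.

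**ROC.** The missing non-case group is a fact, but its effect is conditional. Under the assumptions above, a healthy-only AUC overstates separation from other disease by 0 to 0.27, and a 30+30 pooled AUC by 0 to 0.14. At f of 0.25 or less, neither gap exceeds the 95% half-width. These figures show how far the choice of comparator could matter; they do not predict what the study will find. On its own the ROC omission is a modest defect of specification.

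**What to change.** 1. Reconcile sections 6, 6.1, 7, 7.1 and 7.2 on whether patients with milder asthma and with nasal polyposis can be enrolled.
2. In sections 6.1 and 10.2, define ROC cases as SEA and/or EGPA and limit the ROC to serum.
3. Report two unpooled AUCs with 95% CIs: SEA/EGPA against the other recruited patients, giving their number and mix of diagnoses, and SEA/EGPA against healthy controls, labelled a discovery contrast. Separate AUCs for SEA and for EGPA are optional.
4. Name the cases and non-cases of the section 6 ROC. It need not be ranked.

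The cost is wording, best settled before any AUC is computed. For a serum ROC no further participants or samples are needed beyond the 120 planned. The downside is that the AUC against other patients may be less favourable and is imprecise, with a half-width of about 0.06 to 0.12 at 60 against 30, and wider if fewer than 30 others are recruited. It also comes from a mixed comparator group and remains a pilot estimate.
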